session, providing breaks if needed. If necessary due to participant burden, we will schedule a second assessment session. We will prioritize the order of measures administered to ensure that in all cases the anger outcome measures (OAS-M, STAXI-2, and ACQ), and the Outcomes Questionnaire are completed. Telephone assessments will be used if participants are unable to come in for assessments. Every attempt will be made to perform post-treatment and follow-up assessments within one week of their scheduled date.

Table 1. Schedule of Assessments

Domain	Screening	Pre-Tx	Sessions 4 and 8	Post-Tx	Follow-up (3 and 6 months)
Inclusion/exclusion Criteria					
SCID	X				
CAPS	X			X	X
Sample Characterization					
SNAP-2		X			
CTQ		X			
Combat Exposure		X			
BSI		X	X	X	X
BAM (Use subscale)		X			X
Anger					
OAS-M*		X	X	X	X
STAXI-2*		X	X	X	X
ACQ*		X		X	X
DAR (weekly)					
Function/QOL					
LIFE psychosoc		X		X	X
OQ		X		X	X
Disability Scale		X		X	X
WHOQOL-BREF		X		X	X
Mediators					
NAS arousal		X	X	X	
NAS cognitive		X	X	X	
NAS behavioral		X	X	X	
Other Measures					
Tx Satisfaction				X	
LIFE Tx section	X			X	X

Clinician administered interviews are in italics. ACQ = Anger Consequences Scale; BAM = Brief Addiction Monitor; BSI = Brief Symptom Inventory; CTQ = Childhood Trauma Questionnaire; DAR = Dimensions of Anger Scale; NAS = Novaco Anger Scale; OAS-M = Overt Aggression Scale Modified; OQ = Outcomes Questionnaire; SNAP-2 = Schedule for Nonadaptive and Adaptive Personality-2nd Edition; STAXI-2 = State Trait Anger Inventory-2; WHOQOL-BREF = The World Health Organization Quality of Life

*Collateral assessments will be administered at pre- and post-treatment

D. 8. *Blinding of Assessments*

All interviewers will be blind to participants' treatment condition. Each of the outcome domains (anger, functioning/quality of life) includes one blinded interview. Prior to the outcome assessments, the interviewer will remind each participant not to reveal his treatment condition. At the post-treatment and follow-up assessments, interviewers will complete questions including whether they think the blind was broken, and to which treatment condition they think the participant was assigned.

D. 9. *Standardization of Assessments*

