Permission will be requested at the time of informed consent to obtain the name and phone number of a close relative, friend, or other person who is likely to maintain contact with the participant, and to contact that person if attempts to contact the participant are unsuccessful. Post-treatment and follow-up assessments will be conducted in person at appointments scheduled for this purpose. An appointment for the three-month follow-up assessment will be made at termination of the study intervention, and for the six-month follow-up at the three-month interview. Participants will receive a letter one week prior to the interview and a reminder call a few days prior. Participants who do not have telephones will be contacted by mail and asked to call for an appointment. Five contact attempts will be made before a participant is considered to be unreachable at that time point. Participants who fail to appear for a scheduled assessment will be contacted by phone, or mail when necessary, for rescheduling. If participants move away during their

participation in the study, or are otherwise unavailable for an in-person interview, we will perform follow-up assessments over the telephone to avoid missing data.

D. 11. Compensation

Participants will be compensated for the time required to complete all assessments. They will be paid \$100 for the pre-treatment baseline assessment and \$60 for the subsequent post-treatment and follow-up assessment periods.

Participants who screen out on the SCID or CAPS or who do not complete the full baseline assessment will be paid \$40 (for partial assessment). Mid treatment assessments (after sessions 4 and 8) will be compensated at \$25. Collaterals will be compensated \$25 for the pre- and post-treatment assessments. Participants can receive their compensation in the form of an electronic funds transfer or gift card. Collaterals will be compensated with gift cards.

E. Treatment

E. 1. Assignment

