All major variables will be screened for inconsistent or abnormal values, and continuous measures will be assessed for skewness and outliers. Transformations to improve normality may be applied to continuous variables. Missing data rates and patterns will be assessed; in particular, missing data rates by treatment group will be studied. Although randomization tends to produce well-balanced treatment samples⁵⁹ analyses will be carried out to determine any baseline differences between the treatment groups on demographic or other prognostic variables, using chi square analyses for discrete variables and ANOVA for continuous ones. If significant treatment group differences are found on potentially important baseline variables, these variables will be covaried in outcome analyses. Data from all randomized study participants will be used to compare the outcome of the two interventions on an intent-to-treat basis. Hypothesis tests will be two-tailed.

Participants will be counted in the intervention group to which they were randomized, regardless of the number of sessions they completed. We will make every attempt to complete a post-treatment and 3 and 6 month follow-up assessments on any participants who do not complete treatment. We will also conduct supplementary analyses including only those cases completing the full 12 sessions.

Aim 1: Investigate the effectiveness of CBI on primary measures of outcome

Hypothesis: Compared to SI, CBI will be associated with significantly larger reductions in anger and aggressive behaviors at post-treatment and at 3 and 6 month follow-ups.

Aim 2: Investigate the effectiveness of CBI on secondary measures of outcome

Hypothesis: Compared to SI, CBI will be associated with significantly more improvement in social functioning, occupational functioning, quality of life, and PTSD symptoms at post-treatment and at 3 and 6 month follow-ups.

For aims 1 and 2, we will use hierarchical linear modeling (HLM) for repeated measures to test for differences due to treatment condition, covarying for the baseline score of the dependent variable⁶⁵. The primary significance test will be the treatment group main

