effect over time, though there will also be a test for the time by treatment interaction. Significant time by treatment interactions will be followed up by post hoc tests at specific assessment points by calculating simple intercepts, simple slopes, and regions of significance. Relevant covariates will be included to adjust for any imbalances across treatment conditions.

Missing data will be dealt with as follows. HLM analyses can include cases with some time points missing. In the primary analysis, we will include all cases with at least 3 of the 5 outcome time points (4 & 8 weeks, posttreatment, and 3 & 6 months) non-missing. Then, we will conduct a sensitivity analysis including all randomized participants, in which any missing outcome values will be filled in with baseline scores, which is an extreme assumption. Consistency of results from the two approaches will bolster the credibility of the primary analysis.

The primary dependent variables for aim 1 are the STAXI-2 Anger Expression Index, and the OAS-M Aggression Scale score. Outcome on these measures is assessed at 4 and 8-week points during treatment, at post-treatment, and at 3 and 6 months follow-up assessments. DVs for aim 2 include two LIFE scales (global social and work functioning), the Outcomes Questionnaire total score, the WHOQOL-BREF total score, and the CAPS total score. Outcome on these measures is assessed at post-treatment and 3 and 6-month follow-up assessments.

For aims 1 and 2 the alpha will be set at .025 to account for multiple dependent variables.

Supplementary post-treatment outcome analyses will be conducted using collateral measures (including the STAXI-II, Anger Control Scale and Modified Overt Aggression Interview). We will calculate Pearson correlations of participant and collateral scales as an indication of agreement. If outcome analyses based on collateral measures are consistent with analyses of participant measures, this would bolster the validity of the participant outcome findings. Divergent findings could be due to multiple factors that could influence the validity of the participant and the collateral reports. In this case we will conduct analyses using integrated collateral and participant scores, calculated by averaging the participant and collateral responses to each item.

Aim 3: (Exploratory) Examine hypothesized mechanisms of action of CBI

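### The primary HLM drops randomized participants with fewer than 3 of 5 outcome assessments, contradicting the plan's all-randomized intent-to-treat statement; the only all-randomized analysis is a baseline fill-in

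*Combined protocol and SAP*

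**What the plan says.** Section 4.G.2 (Data Analysis) sets the general principle: "Data from all randomized study participants will be used to compare the outcome of the two interventions on an intent-to-treat basis". It adds: "Participants will be counted in the intervention group to which they were randomized, regardless of the number of sessions they completed". It also commits to following people who stop therapy: "We will make every attempt to complete a post-treatment and 3 and 6 month follow-up assessments on any participants who do not complete treatment".

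The missing-data paragraph for Aims 1 and 2 in the same section begins: "HLM analyses can include cases with some time points missing". The next sentence restricts the model: "In the primary analysis, we will include all cases with at least 3 of the 5 outcome time points" observed, the five being 4 and 8 weeks, post-treatment, and 3 and 6 months. A sensitivity analysis then covers all randomized participants, but in it "any missing outcome values will be filled in with baseline scores, which is an extreme assumption". Agreement between the two is to support the primary result. The only other supplementary analysis by population is confined to those who completed all 12 sessions.

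The Aim 1 outcomes are measured at all five occasions. The Aim 2 outcomes are measured only at post-treatment, 3 months and 6 months. Section 4.G.3 assumes 80% follow-up of 120 participants.

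**The concern.** The two statements in Section 4.G.2 cannot both describe the primary comparison, and nothing in the document reconciles them. Attending three assessments happens after randomization and may depend on treatment and response, so the primary tests could be run on a selected set and still be reported as intent-to-treat.

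The rule also discards usable data. Someone last seen at the second assessment has two scores that the model could use. No planned analysis uses the observed data of all randomized participants without filling in. Moving from the primary to the sensitivity analysis changes both the population and the missing-data assumption, so a disagreement could not be traced to either one. Agreement would not show what the observed data of everyone randomized say.

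The direction of any bias is open:

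- If poorly responding CBI participants are lost to assessment more often, the rule favours CBI and can reject more often than 2.5%.
- If the same score-driven loss occurs in both arms and CBI works, the rule understates the effect.
- If loss is random, or most of those lost come back, the bias is near zero.

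The planned look at missing-data rates by arm would reveal unequal loss but not correct for it.

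**Working it through.** **1. The plan's own power figure.** Inputs from Section 4.G.3: 120 participants, 80% follow-up (48 per arm), effect .60, two-sided alpha .025, power 90%. With m visits and common correlation ρ, the variance factor is f = (1 + (m − 1)ρ)/m and power ≈ Φ(.60·√(48/(2f)) − 2.241).

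- One time point (f = 1): .60·√24 = 2.939, giving 75.7%.
- Five visits, ρ = .62: f = .696, giving 90.0%. With ρ = .50 power is 94.0%, and with ρ = .70 it is 87.1%.

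The 90% is attainable but cannot be verified, because no correlation is given. The present point does not rest on it.

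**2. How many the rule excludes.** Lost: 120 × .20 = 24. If loss is permanent:

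- all leave before post-treatment: each has at most two scores, so 24 are excluded;
- loss spread evenly before each of the five visits: those leaving before visits 1-3 fail, 24 × 3/5 = 14.4;
- all leave after post-treatment: 0.

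If visits are instead missed independently with probability .2, P(fewer than 3 of 5) = .058, and 120 × .058 = 7.0 are excluded.

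**3. Bias and rejection rate with no true effect (simulation).** The documents give no arm-specific or score-related loss rates, so these are assumed: 26% score-driven loss in CBI and 15% random loss in SI (average 20.5%, close to the plan's 20%). The only arm-specific hint is slightly higher SI retention in the pilot (Section 4.E.4).

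Model: REML random intercept, categorical time, baseline covariate, treatment main effect, two-sided alpha .025, 60 per arm. Assumed correlations are .5 and .6, and log-odds of loss 1.0 and 1.5 per SD. Loss can occur before any of the five visits, the first three, or session 8 and post-treatment only. There were 10,000 replicates per null cell (6,000 for random loss). Monte Carlo error is about 0.001-0.002 SD and 0.2-0.3 percentage points. Bias is in favour of CBI.

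| Loss mechanism | 3-of-5 rule | All observed data |
|---|---|---|
| (a) Last observed score, nobody returns | 0.04-0.11 SD; 3.1-9.7% | 0.00 SD; 2.0-2.7% |
| (a) Half return for the three later visits | 0.02-0.05 SD; 2.2-3.5% | as above |
| (a) 80% return | 0.00-0.02 SD; 2.4-2.7% | as above |
| (b) Current unobserved score, nobody returns | 0.06-0.12 SD; 4.6-10.7% | 0.04-0.10 SD; 3.2-8.1% |
| (b) 80% return | 0.02-0.04 SD; 2.7-3.4% | 0.01-0.04 SD; 2.5-3.4% |
| (c) Random, 26%/15% | no bias | no bias |

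Timing drives row 1. Five visits: 0.036-0.057 SD and 3.1-4.6%. First three: 0.054-0.081 SD and 3.8-5.4%. Session 8 and post-treatment only: 0.079-0.114 SD and 6.2-9.7%. Average numbers excluded (CBI/SI) are about 10/6, 16/9 and 16/9.

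**4. True effect .60, same score-driven loss in both arms (20% overall; 6,000 replicates).** Loss on the observed score: rule .55-.59, all observed data .60. Loss on the unobserved score: rule .54-.57, all observed data .55-.59.

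**5. What the baseline fill-in does to a true .60 under random loss.** The share of visits missing among those lost is .6 if loss is spread evenly, since (5+4+3+2+1)/25 = .6, and 1.0 if all leave before visit 1.

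- 20% loss in each arm: .60 × (1 − .2 × .6) = .528, or .60 × .8 = .48.
- 26% CBI and 15% SI, with SI improving s SD, spread evenly: (1 − .156)(s + .6) − (1 − .09)s = .473 at s = .5 and .440 at s = 1.0.
- Same rates, all before visit 1: .74(s + .6) − .85s = .389 at s = .5 and .334 at s = 1.0.

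**6. Aim 2.** There are two possible readings.

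- Three of the three visits at which the outcome exists: 120 × .8³ = 61.4 retained with independent 80% attendance, or 120 × .8 = 96 with permanent 20% loss.
- Three of the five named occasions, two of which measure no Aim 2 outcome: with independent 80% attendance about 7.0 are excluded, and 120 × (.0579 − .008) = 6.0 of these have at least one Aim 2 score.

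**The case against.** The plan is open about the rule, states it in advance and pairs it with an analysis of all randomized participants. The general statement can be read as a principle about assigned arm that the missing-data paragraph makes operational. This does not resolve the conflict: the statement speaks of data from all randomized participants in the comparison itself, and the primary analysis does not use them.

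The stronger objection is that the effect may be small. Stopping therapy excludes nobody by itself, since the three later assessments planned for treatment non-completers already meet the rule. Section 4.D.7 adds "Telephone assessments will be used if participants are unable to come in for assessments", and Section 4.D.10 adds "Five contact attempts will be made before a participant is considered to be unreachable at that time point". Contact attempts at each time point make intermittent missingness plausible, in which case about 7 rather than 14-24 participants are excluded. With 80% returning, the rejection rate is practically nominal; with half returning, its range spans 2.5%. All of that stands. Even so, the plan itself expects only 80% follow-up.

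The largest inflation needs unequal, score-driven loss with nobody returning, which the documents do not establish. The understatement under equal loss also depends on the model: in a different scenario, where one outcome-related rule after session 8 applied to both arms, the bias was under 0.01 SD.

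On Aim 2, the sentence names five occasions, so the 3-of-3 reading is not literal, and 61 is a lower extreme rather than an expectation. The plan's silence on how the rule applies to Aim 2 remains.

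**Conclusion.** The concern holds and should be fixed. The contradiction is in the text and needs no assumption: the primary model selects on assessment completion after randomization, although the plan promises to use everyone randomized and acknowledges that HLM can handle incomplete cases. The Aim 2 ambiguity is likewise textual.

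The size and direction of the bias are not known from the documents. Under the assumed unequal, score-driven loss it ranges from nearly nil to about 0.1 SD in favour of CBI, with up to roughly 10% rejection at a nominal 2.5%. With equal score-driven loss and a true .60, the rule can give .54-.59. Under random loss there is no bias.

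A likelihood analysis of all observed data is unbiased if data are missing at random and the model is correct. If loss depends on unobserved scores, it reduces the bias but does not remove it. The baseline fill-in cannot stand in for it, because under random loss it pulls a true .60 to between .33 and .53 in the cases worked above.

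**What to change.** 1. Delete the 3-of-5 rule from the primary analysis in Section 4.G.2. Fit the primary HLM for Aims 1 and 2 by likelihood to all observed outcomes from every randomized participant, and state the missing-at-random assumption. Say how participants with only a baseline score are handled, for example by modelling baseline as a response. Keep the 3-of-5 set as a supplementary analysis. This also removes the Aim 2 ambiguity.
2. Because missing at random may fail, supplement the baseline fill-in with a sensitivity analysis in the same all-randomized population that varies only the missing-data assumption. Delta-adjusted multiple imputation is one option.
3. Minor: Sections 4.D.7 and 4.D.11 and Table 1 tie the first two assessments to sessions 4 and 8, while Section 4.G.2 places them at 4 and 8 weeks. Reconcile the wording.

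The cost is SAP wording and a little more analysis work, with no new data. The estimate may move in either direction.

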Two measures will serve as the primary outcome measures for anger: the Anger Expression Index (AXI) from the State-Trait Anger Inventory-2⁴⁴ and the Aggression Scale score from the Overt Aggression Scale-Modified⁴⁵.

STAXI-2: The STAXI-2 ⁴⁶ is a revision of Spielberger's State-Trait Anger Expression Inventory (STAXI), expanded from 44 to 57 items on the basis of over a decade of research. It is a self-report questionnaire consisting of six scales and an Anger Expression Index (AX). Scales include State Anger, which measures the intensity of current angry feelings; Trait Anger, which measures the frequency of angry feelings over time; Anger Expression-Out, which measures how often angry feelings are expressed in verbally or physical aggressive behavior; Anger Expression-In, which measures how often angry feelings are experienced but not expressed; Anger Control-Out, which

measures how often a person controls the outward expression of angry feelings; and Anger Expression-In, which measures how often a person tries to control angry feelings by calming down. The Anger Expression Index is an overall measure of the expression and control of anger based on responses to the two anger expression and the two anger control subscales. The original STAXI and the STAXI-2 have been widely used in treatment studies, including veteran samples^{25, 27, 28} and has substantial psychometric evidence, including convergent and discriminant validity, and sensitivity to change⁴⁵.

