Dimensions of Anger Response (DAR): The DAR, developed by Novaco⁵⁰ is a 7-item self-report measure of anger reactions. A more recent report on the psychometrics of the DAR showed it to be unidimensional, reliable, and sensitive to change over time^{50, 51}. The DAR will be administered at each session.

D. 3. Collateral Assessments

Data from collaterals can provide an important additional perspective on treatment outcome. We will ask participants if they are willing to have a significant other complete

anger outcome measures for the purpose of providing an additional perspective on amount and types of change following treatment. For each participant who agrees, we will ask him or her to identify the person or persons with whom they spend the most time, and/or have sufficient interactions to be familiar with the participant's typical behavior. A minimum of 5 hours of contact a week will be required to qualify as a collateral reporter. If there are multiple possible candidates, we will ask the participant to identify the one who they believe would be the best able to provide a valid assessment of their anger. Participants may take up to two days to consider the request and to discuss with the potential collateral. If the participant agrees, s/he will be asked for permission to contact the nominated individual as part of the consent process. Although encouraged, identification of collaterals will not be required for inclusion in the study. Collaterals will be fully informed of the study requirements and if they are willing to participate, will be asked to sign informed consent. Collaterals will also be provided with the Notice of VHA Privacy Practices. They will be asked to complete the STAXI-II (excluding the state anger scale), the Sheehan Disability Scale, and the Overt Aggression Scale interview at pre- and posttreatment. These measures will be adapted from first to third person for this purpose. We will record demographic information, the nature of the relationship (e.g. spouse, family member, friend) and the average number of hours of contact per week with the participant. At post-treatment, we will also administer a collateral version of the Patient Satisfaction form.

D. 4. Secondary Outcome Measures: Functioning and Quality of Life

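### Pearson correlation says little about whether collaterals corroborate the self-reported effect; estimate the participant-minus-collateral difference by arm, and report outward and inward STAXI-2 scales separately

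*Combined protocol and SAP*

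**What the plan says.** Section D.3 (Collateral Assessments) asks consenting collaterals to "complete the STAXI-II (excluding the state anger scale), the Sheehan Disability Scale, and the Overt Aggression Scale interview at pre- and posttreatment". It adds: "These measures will be adapted from first to third person for this purpose". Participants need not nominate a collateral, and a collateral must have at least 5 hours of contact a week with the participant.

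Removing only the state scale leaves all four subscales that feed the Anger Expression Index, one of the two primary outcomes. Section D.2 describes that index as "based on responses to the two anger expression and the two anger control subscales". By the same section, Anger Expression-In "measures how often angry feelings are experienced but not expressed", and a further scale "measures how often a person tries to control angry feelings by calming down". D.2 prints the Expression-In label a second time for this last scale. The pilot results in section 3 list a Control In scale, so I read it as Anger Control-In.

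Section 4.G.2 then gives collateral data three uses:

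- Supplementary post-treatment outcome analyses on the collateral measures. If these are consistent with the participant analyses, the plan takes that as support for the participant findings.
- A measure of agreement: "We will calculate Pearson correlations of participant and collateral scales as an indication of agreement".
- If findings diverge, analyses of scores formed by averaging the two reporters item by item.

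The section gives no criterion for consistency and no comparison of the two reporters by arm.

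**The concern.** Participants know which treatment they receive. The STAXI-2 is self-report. The OAS-M is rated by a blinded interviewer, but from an interview with the participant. Collaterals are the only source on anger outside the participant, so their reports are where a shift in CBI self-report alone could show up.

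The agreement statistic should therefore respond to a difference between reporters that differs between arms. Pearson r is not built for that. It is unchanged by a constant gap between reporters and moves little when one arm's self-report shifts.

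The inward subscales raise a second difficulty. If the collateral index shows a smaller effect than the participant index, the reader cannot tell whether the effect is smaller than reported or whether half of the index's subscales cover things a spouse or friend sees only partly. Arousal reduction is a named element of CBI (section E.2), so some of the intended change lies where observation is weakest.

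**Working it through.** The documents give no figure for the collateral analysis, so there is none to reproduce. What follows is an illustration scaled to the trial's own planning values.

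**Inputs**

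- From section G.3: effect size d = 0.60, N = 120, follow-up 80%. This gives 120 × 0.80 = 96 participants, or 48 per arm if the arms are equal.
- Assumed: within-arm SD of 1 for both reporters; within-arm participant-collateral correlation r of 0.3 to 0.7; collaterals for 25% to 100% of the 96. The documents give neither the correlation nor the uptake.
- e is the treatment effect that collaterals see.

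**Step 1: pooled Pearson r.** With equal arms, the covariance is r + de/4 and the variances are 1 + d²/4 and 1 + e²/4. Here d²/4 = 0.36/4 = 0.09.

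- Effect in self-report only (e = 0), r = 0.70: 0.70/√1.09 = 0.67.
- Effect seen by both (e = 0.60), r = 0.70: (0.70 + 0.09)/1.09 = 0.73 (0.725 before rounding).

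| Within-arm r | Seen by both | Self-report only |
|---|---|---|
| 0.3 | 0.36 | 0.29 |
| 0.5 | 0.54 | 0.48 |
| 0.7 | 0.73 | 0.67 |

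The unknown within-arm correlation dominates. An effect present only in self-report gives 0.67 when that correlation is 0.7, which is higher than the 0.54 for an effect seen by both when it is 0.5. Sampling error matters too: with 96 pairs the standard error of r near 0.70 is about (1 − 0.49)/√96 = 0.05, close to the whole difference between the two cases.

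**Step 2: absolute-agreement ICC (concordance form).** For two raters this is twice the covariance, divided by the sum of the variances plus the squared mean difference. The pooled mean difference is (d − e)/2.

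- Self-report only, r = 0.70: 1.40/(1.09 + 1 + 0.09) = 0.64, against Pearson 0.67. At r = 0.5 the coefficient is 0.46, against 0.54 when both see the effect. It separates the cases little better than Pearson does.
- It does detect a constant rater gap. At r = 0.6, a gap of 0, 0.5 or 1.0 SD gives 1.2/(2 + gap²) = 0.60, 0.53 or 0.40, while Pearson stays at 0.60.

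**Step 3: between-arm difference in the participant-minus-collateral gap.** This equals d − e: 0 when both see the effect, 0.60 SD when only self-report shows it. Its within-arm SD is √(2(1 − r)), which is 1 at r = 0.5, so the unadjusted post-treatment 95% half-width is 1.96√(2/n) for n pairs per arm:

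- n = 48 (full uptake): 0.40 SD
- n = 24 (half): 0.57 SD
- n = 12 (a quarter): 0.80 SD

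**Step 4: the planned collateral arm comparison.** No alpha is stated for it; I use two-sided 0.05. The second row assumes that poorly observed items halve the collateral effect.

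| Collateral effect | 25% uptake | 50% | 75% | 100% |
|---|---|---|---|---|
| 0.60 SD | 0.31 | 0.55 | 0.72 | 0.84 |
| 0.30 SD | 0.11 | 0.18 | 0.25 | 0.31 |

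A null collateral index result is therefore plausible even when the effect is real.

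**Step 5: the averaging fallback.** If participants report 0.60 SD and collaterals see nothing, the averaged score has standardised effect 0.30/√((1 + r)/2). That is 0.37 at r = 0.3 and 0.33 at r = 0.7. Averaging keeps an apparent effect and does not show where it came from.

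**The case against.** The strongest reply is that the plan does not judge validity by r. Corroboration rests on whether the collateral outcome analyses are consistent with the participant analyses, and no decision depends on the size of the correlation. In the self-report-only case above, the collateral analysis would estimate 0 against 0.60 SD, which is the divergence the plan looks for. This stands. A reader might infer from the Pearson sentence that the collateral check as a whole cannot show whether the self-report effect is real. The documents do not support that. The between-arm comparison is planned, the overt aggression interview covers observable behaviour, and two of the four index subscales are outward.

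A reader might also infer that collaterals cannot rate the inward scales at all. The protocol gives one-line scale descriptions and no item wording. Efforts to calm down may have visible signs to someone with 5 hours of weekly contact, and the state anger scale has already been removed. Poorly observed is as far as the text goes. For that reason I would not drop these scales.

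A third tempting inference is that a between-arm gap proves under-reporting in CBI. It does not. If a true 0.60 SD effect is half visible to collaterals, the gap differs by 0.30 SD with no reporting bias. Section 4.G.2 itself says that divergence can have several causes on either side.

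Finally, the analysis is supplementary and collaterals are optional, so the stakes are limited. That is correct. What remains is that the only named agreement statistic is poorly suited to its purpose, and that consistency between the two sets of analyses is left to informal judgement.

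**Conclusion.** The point holds in limited form. Pearson r is a weak indication of agreement here: it separates an effect seen by both reporters from one seen only in self-report by about 0.06 to 0.07 across the assumed within-arm correlations. The between-arm difference in the gap separates the same cases by 0.60 SD.

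The planned collateral outcome comparison remains the main check. Its weaknesses are the informal comparison with the participant analysis and an index in which two of four subscales are hard for others to observe.

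The figures rest on equal arms, unit SDs, a 0.60 SD self-report effect and assumed correlations and uptake. The halved collateral effect is an illustration and not an estimate. No primary or secondary test is affected.

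**What to change.** In section 4.G.2:

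1. Replace Pearson r as the agreement measure with the participant-minus-collateral difference, estimated by arm at pre- and post-treatment. Give a confidence interval for the between-arm difference in that gap. Keep an absolute-agreement ICC as a secondary figure for overall rater gaps only.
2. Report collateral Anger Expression-Out and Anger Control-Out separately from the two inward subscales, and keep the inward ones.
3. State in advance that a between-arm gap will be read as divergence consistent with reporting bias or limited observability, and not as proof of bias.

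The gap estimate should also be shown beside any averaged participant-collateral score, so that averaging does not hide divergence.

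The cost is SAP wording and a few lines of supplementary analysis on data already planned at both time points. The limit is precision: at half uptake or less the interval for the gap will be wide, and the report should say so.
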